## 11.3 Site monitoring

Before study initiation, at a site initiation visit or at an investigator's meeting, a Novartis/delegated CRO representative will review the protocol and data capture requirements (i.e., eCRFs) with the investigators and their staff. During the study, Novartis employs several methods of ensuring protocol and Good Clinical Practice (GCP) compliance and the quality/integrity of the sites' data. The field monitor will visit the site to check the completeness of patient records, the accuracy of data capture / data entry, the adherence to the protocol and to GCP, the progress of enrollment, and to ensure that study treatment is being stored, dispensed, and accounted for according to specifications. Key study personnel must be available to assist the field monitor during these visits. Continuous remote monitoring of each site's data may be performed by a centralized Novartis/delegated CRO. Additionally, a central analytics organization may analyze data and identify risks and trends for site operational parameters, and provide reports to Novartis clinical teams to assist with trial oversight.

The investigator must maintain source documents for each patient in the study, consisting of case and visit notes (hospital or clinic medical records) containing demographic and medical information, laboratory data, electrocardiograms, and the results of any other tests or assessments. All information on CRFs must be traceable to these source documents in the patient's file. The investigator must also keep the original informed consent form signed by the patient (a signed copy is given to the patient).

The investigator must give the monitor access to all relevant source documents to confirm their consistency with the data capture and/or data entry. Novartis monitoring standards require full verification for the presence of informed consent, adherence to the inclusion/exclusion criteria,

documentation of SAEs, and of data that will be used for all primary variables. Additional checks of the consistency of the source data with the CRFs are performed according to the study-specific monitoring plan. No information in source documents about the identity of the patients will be disclosed.

# 12 Data analysis and statistical methods

The data will be analyzed by Novartis and/or a designated CRO.

The primary endpoint analysis will include the primary endpoint (Week 16) and results of retreatment for proptosis non-responders, after all patients have completed the Week 40 visit assessment. This will support potential regulatory filing as described in Section 4.4. A final analysis is planned at the EOS once all patients have completed their EOS visit. There may be analyses in addition to Week 40 and Week 108 timepoints to support regulatory filings.

Any data analysis carried out independently by the investigator should be submitted to Novartis before publication or presentation.

## 12.1 Analysis sets

The Randomized Set consists of all randomized participants. Unless otherwise specified, misrandomized participants (mis-randomized in IRT) will be excluded from the randomized set. Mis-randomized participants are defined as those participants who were mistakenly randomized into the IRT prior to the site confirming all eligibility criteria had been met and to whom no study medication was given. Mis-randomized participants are treated as screen failures.

The Full Analysis Set (FAS) comprises all patients to whom study treatment has been assigned. Patients will be analyzed according to the treatment they have been assigned to.

The Safety Set includes all patients who received at least one dose of study treatment/reference treatment. Patients will be analyzed according to the study treatment received.

## 12.2 Patient demographics and other baseline characteristics

Demographic and other Baseline data including disease characteristics will be listed and summarized descriptively by treatment group and in total for the FAS.

Categorical data will be presented as frequencies and percentages. For continuous data, mean, standard deviation, median, minimum, and maximum will be presented.

Relevant medical histories and current medical conditions at Baseline will be summarized by system organ class (SOC) and preferred term (PT), and by treatment group.

## 12.3 Treatments

The Safety Set will be used for the analyses below. Categorical data will be summarized as frequencies and percentages. For continuous data, mean, standard deviation, median, minimum, and maximum will be presented.

Concomitant medications and significant non-drug therapies prior to and after the start of the study treatment will be listed and summarized according to the anatomical therapeutic chemical (ATC) classification system, by treatment group.

## 12.4 Analysis of the primary endpoints/estimands

During scientific advice sessions, the FDA and the EMA expressed different preferences regarding the primary and secondary endpoints and their ordering. Therefore, this study will have 2 different analysis strategies and corresponding endpoint definitions, Plan A is intended for the EMA submission and Plan B is intended for the submission to FDA. The plan used for other health authorities will be based on local decisions.

## Plan A (EU)

The primary objective of this study is to demonstrate the effect of secukinumab 300 mg compared to placebo on the overall responder rate at Week 16.

The primary endpoint is the proportion of patients achieving overall response at Week 16 defined as follows:  $\geq 2$  point reduction in CAS AND  $\geq 2$  mm reduction in proptosis from Baseline in the study eye, provided there is no corresponding deterioration in CAS or proptosis ( $\geq 2$  point or 2 mm increase, respectively) in the fellow (contralateral) eye.

## Plan B (FDA)

The primary objective is to demonstrate the effect of secukinumab 300 mg compared to placebo on the responder rate in  $\ge 2$  mm reduction of proptosis at Week 16.

The primary endpoint is the proportion of patients achieving response in reduction of proptosis at Week 16 defined as follows: reduction of  $\geq 2$  mm from Baseline in the study eye without deterioration ( $\geq 2$  mm increase) of proptosis in the fellow eye.

## 12.4.1 Definition of primary endpoints/estimands

For the definition of primary and secondary estimands, see Section 2.1 and Section 2.2.

## 12.4.2 Statistical model, hypothesis, and method of analysis

The null hypothesis to be rejected is that there is no difference in marginal response rates for patients with secukinumab vs. patients with placebo after 16 weeks.

Let pj denote the probability of a response at 16 weeks for treatment group j, j=0, 1 where

- 0 corresponds to placebo
- 1 corresponds to secukinumab

The following hypotheses will be tested:

H0:  $p_1 = p_0$  versus HA:  $p_1 \neq p_0$ 

The primary analysis will be performed comparing treatments with respect to the primary endpoint in a logistic regression model with treatment group and stratum (i.e., smoking status) as factors and Baseline proptosis as covariate. Difference in marginal response proportions between treatments and its 95% confidence interval (CI) will be imputed using the marginal standardization method, details will be provided in the SAP. The primary analysis will be based on the FAS and will be performed when all patients have completed the Week 16 assessment.

#### **Testing strategy**

The following hypotheses will be included in the testing strategy, and type-I-errors will be set such that a family-wise-type-I-error of  $\alpha = 0.05$  is kept.

#### Plan A

Primary objective:

H1 Secukinumab 300 mg is not different to placebo regimen with respect to the proportion of patients achieving overall response (as defined above) at Week 16.

Key secondary objectives:

- H2 Secukinumab 300 mg is not different to placebo regimen with respect to the proportion of patients achieving a CAS response defined as  $a \ge 2$ -point reduction at Week 16 without corresponding deterioration in CAS ( $\ge 2$ -point increase) in the fellow eye.
- H3 Secukinumab 300 mg is not different to placebo regimen with respect to the proportion of patients achieving a proptosis response defined as  $a \ge 2$  mm reduction in proptosis at Week 16 without corresponding deterioration in proptosis ( $\ge 2$  mm increase) in the fellow eye.
- H4 Secukinumab 300 mg is not different to placebo regimen with respect to the mean change from baseline in CAS at Week 16.

The family-wise error will be set to  $\alpha = 0.05$  (2-sided), which will be controlled via the proposed fixed testing sequence. The hypothesis for the composite primary objective will be tested first and in case of rejection, H2 and H3 will be tested simultaneously. This can be done without any multiplicity adjustment, as H2 and H3 are the hypotheses for the single components

contained in the primary composite and rejection of  $H_1$  would necessitate the rejection of at least one of the component hypotheses  $H_2$  or  $H_3$ . Then, based on the rejection of  $H_2$  and  $H_3$ , the final test will be performed for  $H_4$ . Further secondary endpoints will be tested outside of the confirmatory framework without adjustments for multiple testing.

#### Plan B

Primary objective:

H1 Secukinumab 300 mg is not different to placebo regimen with respect to the proportion of patients achieving a proptosis response defined as  $a \ge 2$  mm reduction in proptosis at Week 16 without corresponding deterioration in proptosis ( $\ge 2$  mm increase) in the fellow eye.

Key secondary objectives:

- H2 Secukinumab 300 mg is not different to placebo regimen with respect to the proportion of patients achieving a CAS response defined as  $a \ge 2$ -point reduction at Week 16 without corresponding deterioration in CAS ( $\ge 2$  points increase) in the fellow eye.
- H3 Secukinumab 300 mg is not different to placebo regimen with respect to the proportion of patients achieving overall response (as defined above) at Week 16.

H4 Secukinumab 300 mg is not different to placebo regimen with respect to the mean change from baseline in CAS at Week 16.

The family-wise error will be set to  $\alpha = 0.05$  (2-sided), which will be controlled via the proposed fixed testing sequence. Further secondary endpoints will be tested outside of the confirmatory framework without adjustments for multiple testing.

#### 12.4.3 Handling of remaining intercurrent events of primary estimand

Not applicable, all intercurrent events and their handling are defined above.

#### 12.4.4 Handling of missing values not related to intercurrent event

The primary endpoint should in principle be available for all patients who do not discontinue the trial. However, if for any reason the response status is unknown for such a patient, he/she will be counted as a non-responder.

#### 12.4.5 Sensitivity analyses for primary endpoint/estimand

Treatment groups will be compared using a Mantel-Haenszel-Test.

#### 12.4.6 Supplementary analysis

# 12.4.7 The primary analysis will be conducted separately within the two strata.Supportive analyses

An additional Bayesian analysis may be conducted. Posterior distributions of the treatment effect will be derived as a guidance for internal decision making on further development in this indication. Details will be specified in a separate analysis plan.

## 12.5 Analysis of secondary endpoints/estimands

## 12.5.1 Efficacy endpoints

#### Plan A

The 2 components of the primary endpoint, the **CAS response** and the **proptosis response** will be analyzed separately using the same methodology as for the primary endpoint.

## Plan B

The **CAS response** and the **overall response** will be analyzed using the same methodology as for the primary endpoint.

The mean change from baseline in CAS, the mean change from baseline in proptosis and the mean change from baseline in GO-QoL score will be analyzed using a mixed model for repeated measures (MMRM) with factors treatment group and stratum and with baseline as a covariate. Least-square mean differences with corresponding confidence intervals and p-values will be calculated for each visit time point as estimates for the treatment effect.

The proportion of patients achieving response in diplopia and the proportion of patients with an improvement in disease severity at Week 16 will be analyzed analogous to the primary endpoint.

#### 12.5.2 Safety endpoints

For all safety analyses, the Safety Set will be used. All listings and tables will be presented by treatment group.

Safety summaries (tables, figures) include only data from the on-treatment period and followup period with the exception of Baseline data that will also be summarized where appropriate (e.g., change from Baseline summaries). In addition, a separate summary for death including on treatment and post treatment deaths will be provided. In particular, summary tables for AEs will summarize only on-treatment events, with a start date during the on-treatment period (treatment-emergent AEs).

#### Adverse events

All information obtained on AEs will be displayed by treatment group and patient.

The number and percentage of patients with treatment emergent AEs (events started after the first dose of study medication or events present prior to start of double-blind treatment but increased in severity based on PT) will be summarized in the following ways:

- By treatment, primary SOC and PT.
- By treatment, primary SOC, PT and maximum severity.

Separate summaries will be provided for study treatment related AEs, death, SAEs, other significant AEs leading to discontinuation.

The number (and proportion) of patients with adverse events of special interest (AESIs) will be summarized by treatment.

A patient with multiple AEs within a primary SOC is only counted once towards the total of the primary SOC.

#### Vital signs

All vital signs data will be listed by treatment group, patient, and visit/time and if ranges are available, abnormalities (and relevant orthostatic changes) will be flagged. Summary statistics will be provided by treatment and visit/time.

#### **Clinical laboratory evaluations**

All laboratory data will be listed by treatment group, patient, and visit/time and if normal ranges are available abnormalities will be flagged. Summary statistics will be provided by treatment and visit/time.

# 12.7 Interim analyses

Please refer to Section 4.4.

#### **12.8** Sample size calculation

For Plan A (EMA submission), the primary endpoint is the proportion of patients achieving overall response at Week 16 defined as follows:  $\geq 2$  point reduction in CAS AND  $\geq 2$  mm reduction in proptosis from Baseline in the study eye, provided there is no corresponding deterioration in CAS or proptosis ( $\geq 2$  point or 2 mm increase, respectively) in the fellow eye.

For Plan B (FDA submission), the primary endpoint is the proportion of patients achieving response in reduction of proptosis at Week 16 defined as follows: reduction of  $\geq 2$  mm from Baseline in the study eye without deterioration ( $\geq 2$  mm increase) of proptosis in the fellow eye.

The sample size calculation is given for the primary endpoint of the EMA strategy Plan A that takes into account both CAS and proptosis response rates. For the FDA strategy Plan B, the deliberations given for the secondary endpoint below apply, which in effect follow the same principles as the primary endpoint.

#### 12.8.1 **Primary endpoint**

In the Phase 3 teprotumumab study (Douglas et al 2020) for which data are available on active and placebo arms, the percentage of patients achieving a reduction of 2 mm or more in proptosis and a reduction of 2 points or more in CAS in the study eye at Week 24 was 78% for patients receiving teprotumumab and 7.1% for patients receiving placebo (p < 0.001). In the Phase 2 clinical trial of teprotumumab (Smith et al 2017), the corresponding responder rates at Week 24 were 69% (teprotumumab) vs. 20% (placebo) (p < 0.001).

For the current study, we are hypothesizing response rates of 60% for secukinumab vs. 20% for placebo. A response rate of 60% is considered clinically meaningful given the medical need for effective treatment with a therapy of active, moderate to severe TED that does not carry the toxicity risks of current treatment alternatives, e.g., high dose i.v. corticosteroids. With this response rate and the expected safety profile of secukinumab to be similar to that already established, the response will fall in line with a favorable benefit-risk assessment.

Under these assumptions, 35 patients per treatment arm (70 patients in total) are required to achieve a power of 90% to demonstrate superiority at a significance level of 0.05 using the 2-group continuity corrected Chi-squared test of equal proportions.

In case of deviations in the group proportions/percentages for the primary endpoint and keeping the number of patients per group at 35 and the significance level constant, the following table includes the differing power scenarios for the planned study. They show a robust statistical basis for this trial in terms of power.

Placebo response	Secukinumab response	Power
0.175	0.60	0.94
0.20	0.60	0.90
0.225	0.60	0.85

#### 12.8.2 Secondary endpoints

For the key secondary endpoints included in the fixed testing sequence described above, treatment effects in about the same order of magnitude as for the primary endpoint are expected; therefore, the power for these endpoints should also be similar and should be adequate.

# 13 Ethical considerations and administrative procedures

## 13.1 Regulatory and ethical compliance

This clinical study was designed and shall be implemented, executed and reported in accordance with the ICH Harmonized Tripartite Guidelines for Good Clinical Practice, with applicable local regulations (including European Directive 2001/20/EC, US CFR 21), and with the ethical principles laid down in the Declaration of Helsinki.

## 13.2 Responsibilities of the investigator and IRB/IEC

Before initiating a trial, the investigator/institution must obtain approval/favorable opinion from the IRB/IEC for the trial protocol, written informed consent form, consent form updates, patient recruitment procedures (e.g., advertisements) and any other written information to be provided to patients. Prior to study start, the investigator is required to sign a protocol signature page confirming his/her agreement to conduct the study in accordance with these documents and all of the instructions and procedures found in this protocol and to give access to all relevant data and records to Novartis monitors, auditors, Novartis Quality Assurance representatives, designated agents of Novartis, IRBs/IECs, and regulatory authorities as required. If an inspection of the clinical site is requested by a regulatory authority, the investigator must inform Novartis immediately that this request has been made.

## 13.3 Publication of study protocol and results

The protocol will be registered in a publicly accessible database such as clinicaltrials.gov and as required in EudraCT. In addition, after study completion (defined as last patient last visit) and finalization of the study report the results of this trial will be submitted for publication and posted in a publicly accessible database of clinical trial results, such as the Novartis clinical trial results website and all required Health Authority websites (e.g., Clinicaltrials.gov, EudraCT etc.).

For details on the Novartis publication policy including authorship criteria, please refer to the Novartis publication policy training materials that were provided to you at the trial investigator meetings.

## 13.4 Quality control and quality assurance

Novartis maintains a robust Quality Management System (QMS) that includes all activities involved in quality assurance and quality control, to ensure compliance with written Standard Operating Procedures as well as applicable global/local GCP regulations and ICH Guidelines.

Audits of investigator sites, vendors, and Novartis systems are performed by auditors, independent from those involved in conducting, monitoring or performing quality control of the clinical trial. The clinical audit process uses a knowledge/risk based approach.

Audits are conducted to assess GCP compliance with global and local regulatory requirements, protocols and internal SOPs, and are performed according to written Novartis processes.

# 14 **Protocol adherence**

This protocol defines the study objectives, the study procedures and the data to be collected on study patients. Additional assessments required to ensure safety of patients should be administered as deemed necessary on a case by case basis. Under no circumstances including incidental collection is an investigator allowed to collect additional data or conduct any additional procedures for any purpose involving any investigational drugs under the protocol, other than the purpose of the study. If despite this interdiction prohibition, data, information, observation would be incidentally collected, the investigator shall immediately disclose it to Novartis and not use it for any purpose other than the study, except for the appropriate monitoring on study patients.

Investigators ascertain they will apply due diligence to avoid protocol deviations. If an investigator feels a protocol deviation would improve the conduct of the study this must be considered a protocol amendment, and unless such an amendment is agreed upon by Novartis and approved by the IRB/IEC and Health Authorities, where required, it cannot be implemented.

# 14.1 Protocol amendments

Any change or addition to the protocol can only be made in a written protocol amendment that must be approved by Novartis, health authorities where required, and the IRB/IEC prior to implementation.

Only amendments that are required for patient safety may be implemented immediately provided the health authorities are subsequently notified by protocol amendment and the reviewing IRB/IEC is notified.

Notwithstanding the need for approval of formal protocol amendments, the investigator is expected to take any immediate action required for the safety of any patient included in this study, even if this action represents a deviation from the protocol. In such cases, Novartis should be notified of this action and the IRB/IEC at the study site should be informed according to local regulations.

# 16 Appendices

## 16.1 Appendix 1: Clinically notable laboratory values and vital signs

The following criteria will be used to define expanded limits and notable abnormalities of key laboratory tests. Notable values for blood pressure and pulse are presented in Section 8.4.

No specific action is pre-defined within this protocol to respond to specific abnormal laboratory values, as it will be decided by the Investigator/qualified site staff whether and which specific action needs to be taken to respond to any abnormal values, taking into account the overall status of the patient. For additional information please refer to the laboratory manual.

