## 6.5.1 Follow-up for toxicities

Not applicable.

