# 9 Study discontinuation and completion

# 9.1 Discontinuation and completion

# 9.1.1 Study treatment discontinuation and study discontinuation

The investigator closely monitors the disease activity of a patient throughout the entire study and must discontinue study treatment or study participation for a given patient if he/she believes that continuation would negatively impact the patient's well-being.

Discontinuation of study treatment for a patient occurs when study treatment is stopped earlier than the protocol planned duration and can be initiated by either the patient or the investigator.

Study treatment must be discontinued under the following circumstances:

- Subject decision.
- If any of the following (evidence of disease progression) occurs in the study eye or fellow (contralateral) eye:
  - Compressive optic neuropathy that in the opinion of the investigator requires urgent surgical intervention or medical treatment with glucocorticoids
  - Severe corneal injury that requires surgical treatment
  - Severe/major loss of vision defined as a decrease of best-corrected visual acuity to below 0.1 (Snellen equivalent of 20/200)
  - Other abnormalities not here specified but that the investigator determines would require study treatment discontinuation
- Emergence of the following AEs:
  - Any severe or SAE that is not compatible with administration of study medication, including AEs that require treatment with an unacceptable concomitant medication.

- Onset of lymphoproliferative disease or any malignancy, except for treated basal cell carcinoma, treated actinic keratoses, treated *in situ* carcinoma of the cervix or non--invasive malignant colon polyps which are being or have been removed.
- Life-threatening infection.
- Severe hypersensitivity reaction or anaphylactic reaction.
- Any laboratory abnormalities that in the judgment of the investigator are clinically significant and are deemed to place the patient at a safety risk for continuation in the study (a general guidance on clinically notable laboratory values is provided in Appendix 1).
- Pregnancy.
- Use of any biologic immunomodulating agent except secukinumab.
- Other treatment or procedure for TED in case of worsening of the disease.
- Any protocol deviation that results in a significant risk to the patient's safety.

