# 10.2 Additional Safety Monitoring

#### 10.2.1 Liver safety monitoring

To ensure patient safety and enhance reliability in determining the hepatotoxic potential of an investigational drug and/or concomitant medication (e.g., thyrostatic treatment) and/or hyperthyroidism related liver enzyme elevation, a standardized process for identification, monitoring and evaluation of liver events has to be followed.

The following 2 categories of abnormalities / AEs have to be considered during the course of the study (irrespective of whether classified/reported as (S)AE):

- Liver laboratory triggers, which will require repeated assessments of the abnormal laboratory parameter
- Liver events, which will require close observation, follow-up monitoring and completion of the standard base Liver CRF pages

Every liver laboratory trigger or liver event should be followed up by the investigator or designated personnel at the trial site as summarized below (please see Appendix 2 for detailed information).

For the liver laboratory trigger:

• Repeating the liver function test (LFT) within the next week to confirm elevation.

These LFT repeats must be performed using the central laboratory if possible. If this is not possible, then the repeats can be performed at a local laboratory to monitor the safety of the patient. Repeats laboratory must then be performed at central laboratory as soon as possible. If a liver event is subsequently reported, any local LFTs previously conducted that are associated with this event must be reported on the Liver CRF pages.

• If the elevation is confirmed, close observation of the patient will be initiated, including consideration of treatment interruption if deemed appropriate.

For the liver events:

- Repeating the LFT to confirm elevation as appropriate
- Discontinuation of the investigational drug if appropriate
- Hospitalization of the patient if appropriate
- A causality assessment of the liver event via exclusion of alternative causes (e.g., disease, co-medications)
- An investigation of the liver event, which needs to be followed until resolution

These investigations can include serology tests, imaging and pathology assessments, hepatologist consultancies, based on the investigator's discretion. All follow-up information, and the procedures performed must be recorded on appropriate CRF pages, including the liver event overview CRF pages.

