#### Liver function and related variables

ALT (SGPT):	> 3 x upper limit of normal (ULN)
AST (SGOT):	> 3 x ULN
Total bilirubin:	> 2 x ULN
Alkaline phosphatase:	> 2 x ULN

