#### Table 16-3 Liver event and laboratory trigger definitions

\*These events cover the following: hepatic failure, fibrosis and cirrhosis, and other liver damagerelated conditions; the non-infectious hepatitis; the benign, malignant and unspecified liver neoplasms

ALT=alanine aminotransferase, ALP=alkaline phosphatase, AST=aspartate aminotransferase, INR=international normalized ratio, TBL=total bilirubin, UNL=upper normal limit

Table 16-4	Follow-up requirements for liver events and laboratory triggers	
Criteria	Actions required	Follow-up monitoring
Potential Hy's Law caseª	
 
Discontinue the study treatment immediately
 
	ALT, AST, TBL, Alb, pt/INR, ALP and γGT until resolution c
	Hospitalize, if clinically appropriate	(frequency at investigator
	Establish causality	discretion)
	Complete liver CRF	
ALT or AST		
> 8 × ULN	
 
Discontinue the study treatment immediately
 
	ALT, AST, TBL, Alb, pt/INR, ALP and γGT until resolution c
	Hospitalize if clinically appropriate	(frequency at investigator
	Establish causality	discretion)
	Complete liver CRF	
> 3 × ULN and INR > 1.5	
 
Discontinue the study treatment immediately
 
	ALT, AST, TBL, Alb, pt/INR, ALP and γGT until resolution c
	Hospitalize, if clinically appropriate	(frequency at investigator discretion)
	Establish causality	discretion
	Complete liver CRF	

Table 16-4	Follow-up requirements for liver events and laboratory triggers	
	i onow-up requirements for inver events and laboratory triggers	

Criteria	Actions required	Follow-up monitoring
> 5 to ≤ 8 × ULN	Repeat LFT within 48 hours	ALT, AST, TBL, Alb, pt/INR, ALP
	
 
If elevation persists, continue follow up monitoring
 
	_ and γGT until resolution c (frequency at investigator discretion)
	• If elevation persists for more than 2 weeks, discontinue the study drug	,
	Establish causality	
	Complete liver CRF	
> 3 × ULN accompanied by	
 
Discontinue the study treatment immediately
 
	ALT, AST, TBL, Alb, pt/INR, ALP and γGT until resolution c
symptoms b	Hospitalize if clinically appropriate	(frequency at investigator
	Establish causality	discretion)
	Complete liver CRF	
$> 3 \text{ to } \le 5 \times \text{ULN}$	Repeat LFT within the next week	Investigator discretion
(patient is asymptomatic)	
 
If elevation is confirmed, initiate close observation of the patient
 
	Monitor LFT within 1 to 4 weeks

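### Appendix 1 says the protocol pre-defines no action for abnormal laboratory values, but Table 16-4 sets required liver actions, including mandatory stops, at the same thresholds, and Section 9.1.1 cites only Appendix 1

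*Protocol*

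**What the plan says.** Four places in the protocol bear on what a site does with an abnormal liver test.

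- **Appendix 1 (16.1)** says that "No specific action is pre-defined within this protocol to respond to specific abnormal laboratory values". The investigator or qualified site staff decide "whether and which specific action needs to be taken to respond to any abnormal values". Under "Liver function and related variables" it lists ALT and AST above 3 x ULN, and total bilirubin and alkaline phosphatase above 2 x ULN. No exception is made for liver values.
- **Appendix 2 (16.2), Table 16-4**, in its column of required actions, gives a response for each liver criterion. Several rows read "Discontinue the study treatment immediately".
- **Section 9.1.1**, under circumstances in which treatment must stop, has one laboratory item: "Any laboratory abnormalities that in the judgment of the investigator are clinically significant" and deemed a safety risk for continuing. It cites Appendix 1 as guidance. Neither Appendix 2 nor Table 16-4 is mentioned.
- **Section 10.2.1** says that "a standardized process for identification, monitoring and evaluation of liver events has to be followed". Among the steps for liver events it gives "Discontinuation of the investigational drug if appropriate". It describes its steps as a summary and refers to Appendix 2 for detail.

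**The concern.** The Appendix 1 sentence covers the whole protocol and any abnormal value. Table 16-4 does what that sentence says the protocol does not do. Take a patient with ALT at 9 x ULN. Under Appendix 1 the site decides whether to act and how. Under Table 16-4 (ALT or AST above 8 x ULN) treatment must stop at once.

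The routing makes this worse. A site that looks up the stopping rules in 9.1.1 is sent to the appendix that denies any pre-defined action, and not to the one that contains the actions.

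Two things are at stake. The first is conduct: two sites could treat the same result differently and each cite the protocol. There is no data monitoring committee (10.2.3). The situation is foreseeable, since 10.2.1 names thyrostatic treatment and hyperthyroidism as possible sources of liver abnormalities. The second is reporting: adverse events resulting in treatment discontinuation are a safety endpoint, so a real difference in stopping between sites would enter the safety tables.

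**Working it through.** No power, alpha or effect size is involved, and the plan gives no figure to reproduce. The check sets the texts side by side.

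**Step 1. Does Table 16-4 define an action at each Appendix 1 liver threshold?**

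| Analyte | Appendix 1 threshold | Least demanding Table 16-4 response above it |
|---|---|---|
| ALT | > 3 x ULN | > 3 to ≤ 5 x ULN, asymptomatic: repeat test within a week; close observation if confirmed |
| AST | > 3 x ULN | as for ALT |
| Total bilirubin | > 2 x ULN | isolated, no known Gilbert syndrome: repeat within 48 hours; stop if it persists |
| ALP | > 2 x ULN | isolated, no known bone pathology: repeat within 48 hours; establish causality if it persists |

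All 4 of 4 analytes have a required action. The Appendix 1 statement is therefore untrue for every liver value that it lists.

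**Step 2. Which Table 16-4 rows require a stop?**

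| Row | Stop |
|---|---|
| Potential Hy's Law case | immediate |
| ALT or AST > 8 x ULN | immediate |
| ALT or AST > 3 x ULN with INR > 1.5 | immediate |
| ALT or AST > 3 x ULN with symptoms | immediate |
| ALT or AST > 5 to ≤ 8 x ULN | if it persists more than 2 weeks |
| Isolated bilirubin > 2 x ULN | immediate once persistence is shown |
| Jaundice | immediate |
| ALT or AST > 3 to ≤ 5 x ULN, asymptomatic | none |
| Isolated ALP > 2 x ULN | none |
| Bilirubin > 1.5 to ≤ 2 x ULN, asymptomatic | none |
| AE potentially indicative of liver toxicity | to be considered only |

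Laboratory-based rows with a stop: 4 immediate + 2 after persistence = 6. Jaundice also carries a stop, but Table 16-3 defines it as a clinical event, so it lies outside a sentence about laboratory values. Four rows have no required stop. Total: 6 + 1 + 4 = 11 rows. The row for enzymes above 3 x ULN with symptoms is partly clinical, but it still turns on a laboratory threshold.

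**Step 3. Could the stops in Table 16-4 be read as discretionary?** The table marks discretion where it intends it: hospitalization is mostly qualified by clinical appropriateness, and the last row says only to consider interrupting or stopping. The stop lines in the six rows have no such qualifier, beyond the persistence condition in two of them.

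**Step 4. Does Section 9.1.1 resolve the conflict?** No. Its laboratory item depends on judgment and refers to Appendix 1 alone.

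**The case against.** The strongest reply is that Appendix 1 exists to flag notable values (SAP 2.8.3 reuses the same list for that purpose) and that the dedicated liver section tells sites that a standardized process is mandatory and sends them to Appendix 2. A careful site would follow the specific liver rule over the general sentence. That is plausible, and it lowers the risk. It does not remove the conflict, because the sentence claims to cover the whole protocol, makes no liver exception, and is the place to which 9.1.1 points.

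A reader might infer more than the documents support:

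- *That 10.2.1 is a third competing rule.* It summarizes events of mixed force: some require a stop, some a stop after persistence, some none. It also refers to Appendix 2. Its conditional wording is loose where the table is firm, but that is a secondary point.
- *That 9.1.1 itself contradicts Table 16-4.* It does not claim to be exhaustive, and a judgment-based item can stand beside specific rules. The fault is the missing reference to Appendix 2.
- *That the "Not applicable" in 6.5.1 denies liver follow-up.* That entry sits under dose escalation and modification, where adjustments are not permitted. It does not cancel a separate liver section and appendix.
- *That a patient would receive three further weekly doses, between the Week NR16 and NR20 chemistry draws, before another test.* That assumes no test in between, although Table 16-4 and 10.2.1 require repeats within 48 hours or a week for several of these findings.
- *That calling a stop mandatory or discretionary alters the endpoint.* SAP 2.1.1.5 derives discontinuation due to an AE from the drug-withdrawn entry, so only a real difference in stopping would matter.

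**Conclusion.** The contradiction between Appendix 1 and Table 16-4 is real. It covers all four liver analytes in Appendix 1 as regards required action, and six laboratory-based rows as regards discontinuation. For ALP it concerns the repeat test and work-up only, since isolated ALP carries no stop. The one-sided reference in 9.1.1 adds to it.

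The conclusion rests on the ordinary meaning of the text and needs no numerical assumption. Its practical effect is unknown, because the documents report no liver events and do not show which text sites used. As a sense of scale only: if the 28 randomized patients were split evenly, 14 per arm, one patient stopped under one reading and not the other would move that arm's discontinuation rate by 1/14, about 7 percentage points. Nothing in the documents shows that this happened.

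This is an inconsistency in safety conduct and reporting. It does not touch the sample size or the efficacy summaries. No view is taken here on which liver rule is clinically right.

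**What to change.** Reconcile Appendix 1, Table 16-4 and the laboratory item in Section 9.1.1 so that a single liver rule applies and 9.1.1 points to it. Align the summary in Section 10.2.1 with the result. The sponsor decides which rule stands; the texts then need to agree, whichever way that goes.

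The cost is a clarifying amendment, with wording changes only and no new assessments.

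The SAP reports early termination with 28 patients randomized and 23 in follow-up, so an amendment may come too late to guide dosing. In that case the sponsor should at least state which rule governed when liver-related discontinuations are reported, and compare any liver cases with it. The SAP already provides for listings of laboratory data and of AEs leading to permanent treatment discontinuation, so this needs a short statement and a review of existing listings.
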